8.3.2. Follow-up for Patients Discontinued from Treatment

In the event of a permanent discontinuation of treatment, the patient will be followed up for 30 (+ 7) days after administration of the last dose of treatment for safety assessments.

Follow-up for progression of MDS to higher risk and / or transformation to AML and survival will continue every 6 months for at least one year from start of treatment (Cycle 1 Day 1) with TP-0184.

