13.1.5. Analysis Datasets

The safety analysis set (SAS) is defined as all patients who receive at least one dose of study drug (TP-0184) and will be used for safety analysis and related time to event analyses if applicable.

The DLT analysis set (DAS) is defined as patients evaluable for the determination of dose escalation in Phase 1 who met either one of the following criteria:

1. Experienced a DLT during the first 28 days (the DLT evaluation period)
2. Completed the DLT evaluation period and received at least 80% of planned doses.

Patients who did not meet either of the above criteria are not evaluable for the dose escalation assessment and may be replaced as needed to permit dose escalation. The DAS will be used for DLT related analysis.

The efficacy evaluable analysis set (EAS) is defined as all patients who have baseline data of Hemoglobin value, number of transfusions received in previous 12 weeks before study treatment, have received at least 1 dose of TP-0184, and have at least 1 available post baseline response assessment as per the composite endpoint criteria. The EAS will be used for analyses of response rate and related efficacy analyses.

Pharmacokinetic evaluable analysis set is defined as all treated patients in the trial with sufficient and adequate PK sample data as determined by SDP Oncology.

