Duration of reduction in RBC transfusions for 8 weeks is defined as the time from the assessment date of consecutive 8 weeks with reduction from baseline of RBC transfusions ≥ 4 units to the assessment date of the reduction from baseline < 4 units or increased transfusions frequencies from baseline within a consecutive 8 weeks. For high transfusion burden patient with reduction in RBC transfusion.

The K-M survival curve and K-M median (estimate), along with 2-sided 95% CIs will be provided.

13.1.9.1.2.6. Duration of RBC Transfusion-Free Period ≥ 8 weeks

RBC transfusion-free period ≥ 8 weeks patient is defined as a patient who maintains RBC transfusion-free during consecutive 8 weeks or longer in EAS.

Duration of RBC transfusion-free period ≥ 8 weeks is defined as the time from the assessment date of consecutive 8 weeks without any RBC transfusions to the assessment date of the first documented transfusion in the following visits for RBC transfusion-free period ≥ 8 weeks patients.

The K-M survival curve and K-M median (estimate), along with 2-sided 95% CIs will be provided.

13.1.9.1.2.7. Changes in Neutrophil Count

Hematologic improvement in neutrophil count (HI-N) is defined as patients achieving over any consecutive 8-week (56-day) period and / or decrease in neutrophil levels in EAS.

Change in neutrophils analysis will provide summary statistics of the proportion of patients with hematologic improvement in neutrophil count with 2-sided 95% exact binomial confidence intervals using EAS.

13.1.9.1.2.8. Changes in Platelet Count

Hematologic improvement in platelet count (HI-P) is defined as patients achieving hematologic improvement in platelets over any consecutive 8-week (56-day) period and / or decrease in platelet levels in EAS.

Change in platelet count analysis will provide summary statistics of the proportion of patients with hematologic improvement in platelet count with 2-sided 95% exact binomial confidence intervals using EAS.

13.1.9.1.2.9. Progression to AML

Progression to AML is defined follow the guidelines by IWG Response Criteria for MDS 2006 ([Appendix 6](#)).

Summary statistics of the proportion of patients progressing to AML will be estimated with 2-sided 95% exact binomial confidence intervals based on EAS.

13.1.9.1.2.10. Time to Progression to AML

Time to progression to AML is defined as the time from the date of initial dosing at RP2D to the date of first documented progression to AML using EAS.

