The K-M survival curve and K-M median (if estimable), along with 2-sided 95% CIs will be provided.

13.1.9.1.2.11. Overall Survival

Overall survival is defined as the time from the date of initial dosing at RP2D to the date of death. Patients without documentation of death at the time of analysis will be censored at the date last known to be alive. Overall survival will be analyzed based on SAS patients whose initial dosing is RP2D.

The KM survival curve and K-M median (if estimable), along with 2-sided 95% Cis will be provided.

13.1.9.1.2.12. Hematopoietic Stem Cell Transplant Analysis

Hematopoietic stem cell transplant (HSCT) patients are defined as patients achieving a hematologic response and an HSCT in EAS. Summary statistics of the proportion of

hematopoietic stem cell transplant patients will be estimated with 2-sided 95% exact binomial confidence intervals among hematologic response in EAS.

13.1.9.1.2.13. MRI Imaging Analysis

Summary statistics will be provided based on MRI quantitative results by cohort, study, and overall patients. By-patient listings will be provided.

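### Both AML summaries are restricted to the efficacy-evaluable set, and the Kaplan-Meier analysis of time to AML has no rule for death without AML

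*Protocol*

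**What the plan says.** Protocol 13.1.9.1.2.10 defines time to AML in Phase 2 as the time from "the date of initial dosing at RP2D to the date of first documented progression to AML using EAS". The summary is: "The K-M survival curve and K-M median (if estimable), along with 2-sided 95% CIs will be provided". No censoring rule accompanies it. The next section, on overall survival, does give one: "Patients without documentation of death at the time of analysis will be censored at the date last known to be alive".

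Protocol 13.1.9.1.2.9 handles the proportion differently: "Summary statistics of the proportion of patients progressing to AML will be estimated with 2-sided 95% exact binomial confidence intervals based on EAS".

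The analysis sets are in Protocol 13.1.5. Besides baseline data and one dose, membership of the EAS requires patients to "have at least 1 available post baseline response assessment as per the composite endpoint criteria". The safety analysis set (SAS) needs one dose only and "will be used for safety analysis and related time to event analyses if applicable". Overall survival follows that line: "Overall survival will be analyzed based on SAS patients whose initial dosing is RP2D".

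Under Protocol 8.3.2, follow-up of discontinued patients for "transformation to AML and survival will continue every 6 months for at least one year from start of treatment".

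The SAP keeps AML progression among the endpoints (section 1.2) but adds no method. Its section 2 records that the study was terminated after two patients and plans by-patient listings only.

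**The concern.** There are two separate issues.

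**Analysis set.** The composite criteria that decide EAS membership concern haemoglobin and transfusions over 8 weeks (Appendix 1). They have no bearing on whether a patient is at risk of AML. Every dosed patient is at risk from the first dose, and one who progresses early may leave before any response assessment exists. That patient drops out of numerator and denominator in both AML summaries, which pushes the AML rate down. The AML and survival results then describe different patients, and AML data collected under 8.3.2 in patients outside the EAS go unused.

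**Death before AML.** A patient who dies without AML can no longer develop it. If such deaths are censored in a Kaplan-Meier analysis, one minus the curve estimates AML risk as though nobody died first, and so exceeds the proportion of patients who actually progress. The plan does not say whether deaths are censored, and it names no competing-risk method.

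**Working it through.** The documents give no event count, rate or precision target for AML, so there is no figure to reproduce. What follows shows the likely size of each effect.

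**Inputs (Protocol Appendix 3, IPSS-R outcomes table)**
- Time to 25% AML evolution: 10.8 years (Low), 3.2 years (Intermediate).
- Median survival: 5.3 years (Low), 3.0 years (Intermediate).
- Minimum follow-up: 1 year (8.3.2). Phase 2 size: up to 60 (7.2).

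**Assumption.** Hazards are constant over time. Median survival includes deaths after AML, so the hazard of death without AML is bracketed between the full death hazard and that hazard minus the AML hazard.

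**Hazards per year**
- AML, a = -ln(0.75)/t25: Low 0.0266, Intermediate 0.0899.
- Death, upper d = ln(2)/median survival: Low 0.1308, Intermediate 0.2310.
- Death, lower d = upper d - a: Low 0.1041, Intermediate 0.1411.

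**Formulas**
- Deaths censored: 1-KM = 1 - exp(-a t).
- Death competing: CIF = a/(a+d) x [1 - exp(-(a+d) t)].

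Example, Intermediate at 1 year with upper d: 1-KM = 1 - exp(-0.0899) = 8.6%; CIF = 0.0899/0.3209 x [1 - exp(-0.3209)] = 7.7%.

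| Risk group | Year | 1-KM | CIF (upper d to lower d) | Excess, points |
|---|---|---|---|---|
| Low | 1 | 2.6% | 2.5% | 0.13-0.16 |
| Low | 2 | 5.2% | 4.6-4.7% | 0.5-0.6 |
| Intermediate | 1 | 8.6% | 7.7-8.0% | 0.6-0.9 |
| Intermediate | 2 | 16.5% | 13.3-14.4% | 2.1-3.2 |
| Intermediate | 3 | 23.6% | 17.3-19.5% | 4.2-6.3 |

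Years 2 and 3 lie beyond the guaranteed follow-up.

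**Loss through the EAS.** Two readings of the membership rule bound the effect:
- If one early haemoglobin value counts as a response assessment, few patients are lost, since haematology is scheduled repeatedly from Cycle 1 (Table 6).
- If a completed 8-week window is needed, anyone who progresses and leaves before Day 56 is lost. The share of first-year AML events before Day 56 is [1 - exp(-(a+d) x 56/365.25)] / [1 - exp(-(a+d))]: 16.2-16.4% for Low and 16.9-17.5% for Intermediate.

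In patients: with 60 all at Intermediate risk, about 60 x 7.7% = 4.6 first-year AML cases are expected, and 4.6 x 17.5% = 0.8 would fall before Day 56. Taking 5 cases in 60 for illustration, the all-dosed proportion is 5/60 = 8.3% (exact 95% CI 2.8-18.4%). With one early case dropped it is 4/59 = 6.8% (1.9-16.5%); with two dropped, 3/58 = 5.2% (1.1-14.4%).

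**The case against.** The strongest reply has four parts.

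1. *Early AML is not hidden.* A reader might infer that AML is counted only in patients with a response assessment. The documents do not support that. Protocol 12.1.6.3.6 makes AML an adverse event that will generally be serious, 12.1.6.4.2 requires new cancers to be reported within 24 hours, and 13.1.9.2 tabulates adverse events in the safety population. This stands for AML on treatment or within 30 days of the last dose, which is the treatment-emergent window. What remains is a wrong denominator, and possibly missing cases, in the two AML summaries.

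2. *The proportion is not a Kaplan-Meier estimate.* A reader might infer that the two choices bias one AML incidence figure in opposite directions. They do not: the proportion is crude, deaths stay in its denominator, and censoring of deaths does not touch it. Only the EAS restriction affects it. The two effects can meet only in the time-to-AML analysis, where the plan promises a curve and a median and does not say that 1-KM will be reported as incidence.

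3. *Death is not expressly censored.* This is correct. The plan is silent, and Protocol 13.1 leaves detailed methods to the SAP. The criticism is therefore of an omission. A Kaplan-Meier curve with deaths censored is also a legitimate cause-specific summary if it is labelled as one.

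4. *The Day-56 loss assumes a rule that the plan does not state.* This is also correct. The EAS asks for one available assessment, not a completed window. Scheduled on-treatment marrow first falls at Cycle 4 Day 1, so documented AML may not be spread evenly from Day 0. The 16-18% is a ceiling on one reading, not an estimate.

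None of this gives a reason to prefer the EAS for AML, or to leave death unaddressed.

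**Conclusion.** The point holds as a minor one, in two parts. The EAS is the wrong set for both AML summaries: its entry condition is unrelated to AML risk, and it departs from the set used for overall survival and the one that 13.1.5 associates with time-to-event analyses. The loss cannot be quantified until a response assessment is defined; on the strictest reading it is under one expected patient in 60.

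The missing rule for death affects time to AML only. If deaths are censored, 1-KM is too high by at most about 0.9 points (Intermediate) and under 0.2 points (Low) at one year, and by about 2 to 3 points for Intermediate risk at two years. These figures rest on constant hazards taken from a general IPSS-R table, not from this trial's population. At one year the excess is small beside the sampling error shown above.

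No reported result is affected, since the study ended with two patients and only listings are planned. The point bears on the protocol text and on any reuse of it.

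**What to change.** In Protocol 13.1.9.1.2.9 and 13.1.9.1.2.10, and in any SAP that implements them:

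- Use the safety analysis set (all patients whose initial dosing is the RP2D) for the AML proportion and for time to AML, matching overall survival.
- Report the cumulative incidence of AML with death without AML as a competing event.
- Censor patients alive without AML at their last AML-free follow-up.
- Keep cause-specific Kaplan-Meier as a supplementary analysis if wanted, stating that deaths are censored in it.

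Section 13.1.9.1.1 carries similar methods over to Phase 1, so the same wording should apply there with the Phase 1 safety set.

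The cost is a few lines of text. The methods are in standard software, and the AML and survival follow-up in 8.3.2 already supplies the data.

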To assess change from baseline in the Brief Fatigue Inventory (BFI)	The BFI that measures the severity of fatigue based on the worst fatigue experienced during the past 24 hours

Hematopoietic stem cell transplant (HSCT)	To document the percentage and outcome of patients who have achieved a hematologic response and a hematopoietic stem cell transplant (HSCT) during or following treatment with TP-0184
---	--

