Ph1 PK		X	X	X	X	X	X	X	X					
Ph2 Safety ECG ^g	X					X	X	X	X	X				
Ph2 PK						X	X	X	X	X				
Hematopoietic Stem Cell Transplant														
Overall Survival														
MDS Progression / Transformation to AML														

First dose TP-0184 through Follow-up Visit

- Collect for at least one year from the start of TP-0184 treatment
- Collect for at least one year from the start of TP-0184 treatment

Abbreviations: AE = adverse event; AML = acute myeloid leukemia; BFI = Brief Fatigue Inventory; ECG = electrocardiogram; ECHO = echocardiogram; ECOG = Eastern Cooperative Oncology Group; EOT = end of treatment; MDS = myelodysplastic syndromes; MRI = magnetic resonance imaging; MUGA = Multiple-gated acquisition; NYHA = New York Heart Association; PBMC = peripheral blood mononuclear cell; PK = pharmacokinetics

Note: The following will be collected locally and sent to the central lab: **Cardiac markers, iron panel, Hep-25, IL-6, PBMC-SMAD, BMA-SMAD, BMA-Genetic, TGF-beta-1, PK/Metabolites, Bone marrow biopsy.** Refer to the Laboratory Manual for further details.

^a If a patient discontinues study treatment, an End of Treatment visit should be conducted within 14 days (within 3 days) of the last dose of TP-0184 or within 14 days of the decision to discontinue TP-0184 treatment. If the decision is made at a regular per protocol scheduled visit, that visit may be considered the End of Treatment visit.

^b Patients must have a safety evaluation 30 days (+ 7 days) after the last dose of TP-0184.
^c Survival follow-up is performed every 6 months. Follow-up for progression of MDS to higher risk and / or transformation to AML and survival will continue for at least one year from start of treatment (Cycle 1 Day 1).

^d Informed consent must be obtained prior to conduct of screening evaluations.

^e Review all inclusion and exclusion criteria (Section 8) to determine if patient meets all eligibility criteria for enrollment into the study. Complete Eligibility Form and obtain Medical Monitor approval to enroll patient.

^f Collect and document a complete medical and disease history including initial histologically confirmed, current diagnosis of MDS and signs and symptoms of disease, and 12 weeks of transfusion history.
^g ECHO/MUGA scans will be performed every other cycle, such that days on which MRI scans are avoided.

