8. SELECTION AND WITHDRAWAL OF PATIENTS

8.1. Inclusion Criteria

Each patient must meet the following criteria to be enrolled in this study:

1. A documented diagnosis of lower risk MDS (IPSS-R Low, Intermediate) according to WHO 2016 classification, de novo or secondary.
2. Bone marrow biopsy and/or aspirate performed pre-dose to assess disease status and available for review *prior* to full screening review. If the bone marrow biopsy and/or aspirate is nonproductive or nondiagnostic, the procedure must be repeated. Bone marrow biopsy/aspirate performed \leq 12 weeks prior to baseline will not need to be repeated if results and a minimum of 6 slides are available.
3. Relapsed, refractory/resistant, intolerant, or inadequate response to ESA treatment, as defined by the following:
 - Relapse according to IWG 2006
 - Refractory/resistant – documented non-response or response that is no longer maintained to prior ESA-containing regimen, either as single agent or combination (eg, with G-CSF). ESA regimen must have been either:
 - Recombinant human erythropoietin (rHu EPO) \geq 500 IU/wk for at least 8 doses or equivalent

OR

 - Darbepoetin alpha \geq 300 μ g Q3W for at least 4 doses or equivalent
 - Intolerant – documented discontinuation of prior ESA containing regimen, either as single agent or combination (eg, with G-CSF), at any time after introduction due to intolerance or an adverse event.
 - Inadequate response – in the absence of transfusions support, patients under ESA treatment for at least 12 weeks that do not show a rise in hemoglobin of greater than equal to 1 g/dl.
4. Patients with 5q deletions are allowed only if they have failed or are intolerant to lenalidomide treatment.
 - Failure or intolerance to lenalidomide defined as clinical and cytogenetic responses to according to the international working group 2006 MDS: (1) absence of response; (2) bone marrow progression during treatment with or without prior response; (3) secondary failure (loss of prior hematological response without bone marrow progression); or, (4) intolerance (treatment discontinuation due to AEs, with or without prior response) based on investigator judgement ([Prebet 2017](#)).
5. Previous treatment for anemia with or without RBC transfusion support:
 - a. Low transfusion burden (LTb), defined as requiring less than 4 red blood cell units in the 8 weeks before treatment (and baseline hemoglobin $<$ 9.0 g/dL)

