12.2.2. Survival

Survival status will be collected every 6 months for at least one year from the first dose of TP-0184 treatment (Cycle 1 Day 1).

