In general, when no DLTs are observed in 3 patients at a dose level, the decision is to increase the dose. When 1 DLT is observed in 3 patients, the decision is to stay at the current dose level or to escalate to the higher provisional dose level. When more than 1 DLT is observed in a 3-patient cohort, the decision is to decrease the dose level or to stay at the current level.

**APPENDIX 3. REVISED INTERNATIONAL PROGNOSTIC SCORING
SYSTEM (IPSS-R)**

IPSS-R Cytogenetic Risk Groups*, **

Cytogenetic prognostic subgroups	Cytogenetic abnormalities:
Very good	-Y, del(11q)
Good	Normal, del(5q), del(12p), del(20q), double including del(5q)
Intermediate	del(7q), +8, +19, +17q, any other single or double independent clones
Poor	-7, inv(3)/t(3q)/del(3q), double including -7/del(7q), Complex: 3 abnormalities
Very poor	Complex >3 abnormalities

IPSS-R Prognostic Score Values*

Prognostic variable	0	0.5	1	1.5	2	3	4
Cytogenetics	Very Good	-	Good	-	Intermediate	Poor	Very Poor
BM Blasts (%)	≤2	-	>2 - <5	-	5 - 10	>10	-
Hemoglobin (g/dL)	≥10	-	8 - <10	<8	-	-	-
Platelets (x10 ⁹ /L)	≥100	50 - <100	<50	-	-	-	-
ANC (x10 ⁹ /L)	≥0.8	<0.8	-	-	-	-	-

IPSS-R Prognostic Risk Categories/Scores*

Risk Category	Risk Score
Very Low	≤1.5
Low	>1.5 - 3
Intermediate	>3 - 4.5
High	>4.5 - 6
Very High	>6

IPSS-R: Prognostic Risk Category Clinical Outcomes*

	No. pts	Very Low	Low	Intermediate	High	Very High
Subjects (%)	7012	19%	38%	20%	13%	10%
Survival***	-	8.8	5.3	3.0	1.6	0.8
AML/25%**^	-	NR	10.8	3.2	1.4	0.7

**Median, year.

^Median time to 25% AML evolution.

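### Long-term follow-up does not ask about transplant, so the Phase 2 HSCT proportion can be undercounted; separately, median survival is unlikely to be reached at the one-year minimum follow-up

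*Protocol*

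**What the plan says.** **Transplant.** Protocol section 6.2 (Phase 2), repeated in SAP section 1.2, sets a secondary endpoint on the percentage and outcome of patients with a hematologic response and "a hematopoietic stem cell transplant (HSCT) during or following treatment with TP-0184". Section 13.1.9.1.2.12 analyses it as a proportion among hematologic responders in the efficacy evaluable set, with an exact 95% interval. It plans no analysis of outcome.

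The last three rows of Table 6 (section 7.5) are HSCT, overall survival, and MDS progression or AML. Three collection windows follow them in the extracted text. The first is "First dose TP-0184 through Follow-up Visit"; the other two run for a minimum of one year after starting treatment. Section 8.3.2 sets out what happens after treatment stops: a safety follow-up at 30 (+7) days, and then "Follow-up for progression of MDS to higher risk and / or transformation to AML and survival will continue every 6 months". The minimum duration is one year, counted from Cycle 1 Day 1. HSCT is not in that list.

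**Overall survival.** Section 12.2.2: "Survival status will be collected every 6 months for at least one year from the first dose of TP-0184 treatment". No maximum and no data cut-off are given. Section 13.1.9.1.2.10 (time to AML) states "The K-M survival curve and K-M median (if estimable), along with 2-sided 95% CIs will be provided", and section 13.1.9.1.2.11 (overall survival) has the same sentence with small typographic differences. Patients not known to have died are censored when last known alive. Eligibility (section 8.1) is "A documented diagnosis of lower risk MDS (IPSS-R Low, Intermediate) according to WHO 2016 classification, de novo or secondary". The Appendix 3 table "IPSS-R: Prognostic Risk Category Clinical Outcomes" gives median survival of 5.3 years for Low and 3.0 years for Intermediate risk.

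**The concern.** The transplant endpoint explicitly reaches past the end of treatment, but the data collection appears to stop shortly after it. Starting another treatment for the disease is a listed reason for discontinuing TP-0184 (section 8.3.1), so it is plausible that a transplant would come after the last dose. Anything not collected counts as no transplant, so the error goes one way: the proportion falls. What happened to transplanted patients, beyond survival and AML status, would not be on file.

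For overall survival, the median is the only point estimate named. If it is not reached, the report has a curve but no pre-specified number to quote from it.

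**Working it through.** **1. Transplant windows side by side.**
- Endpoint (6.2): during or after treatment, no end date, percentage and outcome.
- Table 6, HSCT row: first dose to the Follow-up Visit. The row-to-window match is by order, because the table is broken in extraction.
- Table 6, survival and progression/AML rows: at least one year.
- Section 8.3.2, six-monthly contacts: progression/AML and survival only.
- Section 13.1.9.1.2.12: proportion only.

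The Follow Up column of Table 6 carries two footnotes, one for the 30 (+7) day safety evaluation and one for six-monthly survival follow-up. The 30-day reading fits better, for two reasons: HSCT has a different window from the two rows marked as at least one year, and section 8.3.2 leaves HSCT out of the six-monthly list.

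**2. Length of the gap under the 30-day reading.** 30/7 = 4.3 weeks.
- Stops at the planned 24 weeks: covered to 24 + 4.3 = 28.3 weeks, leaving about 52 − 28.3 = 23.7 weeks of the first year uncovered.
- Stops at week 8: covered to about 12.3 weeks. This is an edge case, since response itself needs 8 consecutive weeks.
- Stops after about week 52 − 4.3 = 47.7: no gap within the first year.

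**3. Size of the undercount.** If the true proportion transplanted among responders is p and a fraction q of those transplants fall outside the window, the recorded proportion is p × (1 − q) and the bias is −p × q. The documents give neither p nor q, so no estimate is possible. To show sensitivity only, assume 12 responders (0.20 × 60, the response rate named in the Phase 2 criterion). Each missed transplant then moves the proportion by 1/12 = 8.3 points. Exact 95% intervals are 0 to 26.5% for 0/12, 0.2 to 38.5% for 1/12, and 2.1 to 48.4% for 2/12.

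**4. Overall survival.** The plan states no event count or precision for survival, so there is no figure to reproduce. Assume exponential survival at the Appendix 3 medians m and exactly one year of follow-up for everyone. One-year mortality is 1 − 0.5^(1/m).
- Low: 1 − 0.5^(1/5.3) = 0.123; × 60 = 7.4 deaths.
- Intermediate: 1 − 0.5^(1/3.0) = 0.206; × 60 = 12.4 deaths.

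The Kaplan-Meier median needs half to have died, 30 of 60. The binomial probability of 30 or more is about 1e-12 (Low) and 4e-7 (Intermediate). With n = 10 (5 deaths needed) it is 0.4% and 3.7%.

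Appendix 3 gives general IPSS-R figures, and this population may do worse. With n = 60 and shorter assumed medians, the probability is 0.06% at 2.0 years, 2.7% at 1.5 years and 55% at 1.0 year.

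**5. If follow-up runs past the minimum.** Simulation (4,000 replicates, n = 60, uniform accrual, analysis one year after last entry; accrual durations assumed) gives these probabilities of reaching the median:
- 3.0-year median: 9%, 42% and 78% for accrual over 1, 2 and 3 years.
- 5.3-year median: 1%, 5% and 15%.

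**6. What 12-month survival would give.** Expected values are 79% (Intermediate) to 88% (Low). Exact 95% intervals for n = 60 are 68 to 89% (48 alive) and 77 to 95% (53 alive). For n = 10 they are 44 to 97% (8 alive) and 55 to 99.7% (9 alive).

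**The case against.** **On transplant.** The window rests on a table that did not survive extraction, and the Follow-up Visit could be read as the six-monthly contact, in which case Table 6 would already cover at least a year. The denominator is responders, who may continue beyond 24 weeks, so the gap is shorter for them than for an early dropout. Survival and AML status are followed in any case, so outcome is partly captured.

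These points limit the size of the problem. They do not remove it. Whatever Table 6 means, section 8.3.2 omits HSCT from the long-term contacts and section 13.1.9.1.2.12 plans no outcome analysis, although the endpoint asks for both later transplants and their outcome.

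**On survival.** A reader might infer that one-year follow-up rules out a median altogether and that two secondary endpoints would therefore give no usable result. The documents do not support this. One year is a minimum with no cut-off, and step 5 shows that the median can be reached if follow-up runs longer. The plan already makes the median conditional and promises the curve, from which 12-month survival can be read. The HSCT proportion can also be calculated, though it may be an undercount.

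**On relevance.** SAP section 2 says the study was terminated after two patients and plans by-patient listings only. Neither analysis will be run, so the point matters for correcting or reusing the design.

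**Conclusion.** A minor point that holds. The Phase 2 HSCT endpoint is wider than the data collection that serves it. The direction of error is known (downward); the size is not, because the documents give no transplant rate and no timing. That the gap begins about 30 days after the last dose depends on reading Table 6 in row order and on taking the Follow-up Visit as the safety visit. The omission from section 8.3.2 and the missing outcome analysis do not depend on that reading.

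The survival point is secondary. At the minimum follow-up and the protocol's own medians, about 7 to 12 deaths in 60 are expected against 30 needed, so the median is very unlikely. This assumes exponential survival and general IPSS-R medians; it remains below 3% at an assumed 1.5-year median, but not at 1.0 year. The planned sentence is not an error, and naming a 12-month figure is a small reporting gain.

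**What to change.** **Transplant.** Add HSCT date and outcome to the six-monthly contacts already made for survival and AML, for the same minimum of one year. Align Table 6, section 8.3.2 and section 13.1.9.1.2.12 with the endpoint: say which visit the Follow-up Visit is, list HSCT in long-term follow-up, and state how outcome will be summarised.

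**Survival.** Name 12-month Kaplan-Meier survival with a 95% CI as a reported summary, keep the median where it is reached, and state the follow-up cut-off. Because patients are censored when last known alive and no window is given for the six-monthly contacts, the 12-month contact should fall at or after day 365.

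**Cost.** One added item on an existing follow-up form and a few lines of protocol text, with no new visits. The current SAP has no survival or HSCT analysis to reword, so the change belongs in the protocol, or in any later protocol built on this one.
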